# 1.2 Study Description

This is a prospective, multi-center, active surveillance post-approval study designed to estimate the incidence of post-surgical intraocular inflammation (based upon a specific case definition) in approximately 3,300 eyes that have been implanted with an ACRYSOF IQ RESTOR Toric IOL or ACRYSOF IQ RESTOR multifocal IOL in the US (Cohort 2) for up to 180 days. Active surveillance will be conducted through systematic collection, analysis, and interpretation of all reported cases of post-surgical intraocular inflammation over 4 visits ranging from 1 to 180 days post implantation of the ACRYSOF IQ RESTOR Toric or ACRYSOF IQ RESTOR IOL. The ACRYSOF IQ RESTOR Toric IOL and ACRYSOF IQ

RESTOR IOL are commercially available in the United States. This study will include adults (≥ 22 years of age) with preoperative cataract in the study eye(s). Potential subjects will be screened for enrollment into the study. Those qualifying will be considered enrolled in the study at the time the informed consent form is signed and attend a total of up to 11 scheduled visits. The subject will be considered exposed to treatment at the time of surgery when the investigational product touches the eye.

The study includes two groups of subjects (Cohort 1 and Cohort 2).

Cohort 1: Subjects implanted from November 2018 through July 2020 with ACRYSOF IQ RESTOR +3.0 D Multifocal Toric IOL (Models SND1T3, SND1T4, SND1T5 or SND1T6) or an ACRYSOF IQ RESTOR +2.5 D Multifocal Toric IOLs (Models SV25T3, SV25T4, SV25T5, and SV25T6) in at least one eye.

Note: At time of Protocol Amendment 7, Cohort 1 enrollment is complete.

Cohort 2: Subjects implanted after July 2020 with ACRYSOF IQ RESTOR +3.0 D Multifocal Toric IOL (Models SND1T3, SND1T4, SND1T5 or SND1T6) or an ACRYSOF IQ RESTOR +2.5 D IOL (Model SV25T0) in at least one eye.

Note: This Cohort will include subjects enrolled under Amendment 7 and later.

An overview of the study design is depicted in Figure 7-1 of the protocol, and the schedule of visits is presented in Table 12-1.

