# 2.2 Safety Analysis Set

The safety set includes all eyes with attempted test article implantation (successful or aborted after contact with the eye). The safety set will be the primary analysis set for all safety analyses. Modified safety set includes all eyes with successful test article implantation. The modified safety set will be used for a sensitivity analysis of the primary safety endpoint.

Second eye surgery within 6 months of the occurrence of first cataract surgery will be included in the primary analysis. Second eye surgeries after 6 months of the first surgery are also included. If both eyes of a subject are enrolled in this study, full follow-up information from both eyes will be used in the primary analysis. The above definition applies to both Cohort 1 and Cohort 2.

Unless otherwise specified, analyses described below will be reported only for Cohort 2.

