# 5.3.1 Post-Surgical Intraocular Inflammation

For the primary safety endpoint, the rate (per 1,000 IOL implants) of post-surgical intraocular inflammation (based upon the specified case definition) reported within a 180-day post-surgical period following attempted implantation of study IOLs (Cohort 2) in the United States will be estimated along with the exact two-sided 95% confidence interval. The event rate (per 1,000 IOL implants) is calculated as:

Total # of reported events/Total # of attempted implants x 1,000

An eye with multiple reports of inflammation is only counted once toward the total of the inflammation cases and the one related to device will take precedence. The inflammations related to the device will also be summarized. Event rates will be presented by first eye, second eye, and overall eyes, respectively. A subgroup analysis on the primary safety endpoint will be performed by age groups (22-64 years vs. 65 years or older). If both eyes of a subject are enrolled in this study, full follow-up information for both eyes will be used in the primary analysis.

As sensitivity analyses, cumulative event rates of post-surgical intraocular inflammation (based upon the specified case definition) at 180 days will be provided using Kaplan-Meier estimator for first eyes, second eyes, and overall eyes. The corresponding two-sided 95%

confidence interval of the rates will also be provided. Graphical presentations of the Kaplan-Meier post-surgical intraocular inflammation curves for overall eyes will be included. Kaplan-Meier estimators will be calculated using two different censoring rules as follows:

- 1. Full follow-up information for both eyes is used. If an eye does not have inflammation, then follow-up is censored at the time (days) from each surgery to the last known date in the study for each eye;
- 2. If a subject has a second cataract surgery within 180 days of the occurrence of the first cataract surgery, the follow-up for the first eye will be censored at the time of second surgery, in the case of no inflammation before the second surgery, for calculating rates for first eyes.

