For secondary safety, the rates of Toxic Anterior Segment Syndrome, acute postoperative endophthalmitis, chronic postoperative endophthalmitis, and uncategorized cases of postsurgical intraocular inflammation (based upon the specified case definition) reported within a 180-day post-surgical period following attempted implantation of study IOLs (Cohort 2) in the United States will be estimated for first eyes, second eyes, and overall eyes along with the exact two-sided 95% confidence intervals. An eye with multiple same type of inflammation is only counted once toward the total of that type of inflammation and the one related to device will take precedence. An eye with multiple different types of inflammation is only counted once; the inflammation related to device will take precedence, otherwise the precedence will follow the sequence of TASS, acute postoperative endophthalmitis, chronic postoperative endophthalmitis, and uncategorized cases. Inflammations related to the device will also be reported. Cumulative event rates at 180 days will be provided using Kaplan-Meier estimator as described above for first eyes, second eyes, and overall eyes for the secondary safety endpoints as a sensitivity analysis.

A listing of eyes with all such primary and/or secondary events will be provided, where all multiple inflammations that occurred in one eye will be listed.

A listing of eyes with post-surgical intraocular inflammation and with a corneal edema grade greater than the lowest level (Grade 0 – no stromal or epithelial edema) will be provided.

Summary statistics for the rate (per 1,000 IOL implants) of post-surgical inflammation will be provided by presence of corneal edema for overall, first eyes, and second eyes.

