#### **5.3.2** Adverse Events

The applicable definition of an Adverse Event (AE) is in the study protocol. All AEs occurring from when a subject signs informed consent to when a subject exits the study will

be accounted for in the reporting. A treatment-emergent AE is an event not present prior to exposure to treatment or any pre-existing event that worsens following exposure to treatment. All information obtained on adverse events will be displayed by subject and eye.

The number and percentage of all ocular adverse events and the associated two-sided exact 95% confidence interval, including secondary surgical interventions (SSIs) for either eye, will be tabulated for any event and by preferred term with a breakdown by overall, first eyes, and second eyes. An eye with multiple ocular adverse events of the same preferred term is only counted once toward the total of this preferred term. Adverse events related to the study IOL are referred to as adverse device effects.

Adverse events will be summarized in tables with the following:

- 1. All Adverse Events (Serious and Non-Serious Combined)
  - a. Ocular
  - b. Non-Ocular
- 2. All Adverse Device Effects
  - a. Ocular
  - b. Non-Ocular
- 3. All Serious Adverse Events (including Serious Adverse Device Effects)
  - a. Ocular
  - b. Non-Ocular
- 4. Subject Listings
  - a. Non-Serious Ocular
  - b. Non-Serious Non-Ocular
  - c. Serious Ocular
  - d. Serious Non-Ocular
  - e. Pre-Treatment Adverse Events
  - f. Ocular Adverse Events from Non-Study Eyes
  - g. Secondary Surgical Interventions

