# 12 APPENDIX

 Table 12-1
 Schedule of Study Procedures and Assessments

Procedure/ Assessment	Visit 0 (≤ 40 days pre-surgery 1st eye, ≤ 60 days pre-surgery 2nd eye)	Visit 00 & Visit 00A (surgery)	Visit 1 & Visit 1A (Day 1-2 post surgery)	Visit 2 & Visit 2A (Day 7-14 post surgery)	Visit 3 & Visit 3A (Day 30- 60 post surgery)	Visit 4 & Visit 4A (Day 90 - 180 post surgery)	UNSV
Informed Consent	X						
Demographics	X						
Patient Medical History (Ocular and Nonocular) 	X						
Medications (use of medication prior to, during and post-surgery must be documented) 	X	X	X	X	X	X	X
Inclusion/ Exclusion	X	X					
Adverse Events (Volunteered and Elicited)	X	X	X	X	X	X	X
Device Deficiencies		X	X	X	X	X	X
Subject Reported Symptoms	X		X	X	X	X	X
Best Corrected Visual Acuity (BCVA)	X		X	X	X	X	X
Intraocular Pressure	X		X	X	X	X	X
Problems during surgery		X					
Other Surgical Procedures		X					
Aqueous cell	X		X	X	X	X	X
Aqueous flare	X		X	X	X	X	X
Corneal edema	X		X	X	X	X	X
Corneal haze	X		X	X	X	X	X

Fibrin in the anterior chamber, on the surface of the iris or on the intraocular lens (IOL)	X	X	X	X	X	X
Eyelid edema	X	X	X	X	X	X
Conjunctival hyperemia	X	X	X	X	X	X
Ciliary flush	X	X	X	X	X	X
Corneal precipitates	X	X	X	X	X	X
Hypopyon	X	X	X	X	X	X
Dilated fundus examination	X	X 				
Vitreous cell	X	$X^1$	$X^1$	$X^1$	$X^1$	$X^1$
Vitreous haze	X	X 	X 	X 	X 	X1
Photo documentation		$X^2$	X 	$X^2$	$X^2$	X 
Culture of ocular media		$X^2$	$X^2$	$X^2$	$X^2$	$X^2$

 Required for cases of exacerbated post-surgical intraocular inflammation only.

- Medical History: All ocular history, targeted systemic history
- Concomitant Medications: All ocular medications, targeted systemic medications

*NOTE*: Visits with an "A" refer to visits for the 2nd eye visits for cases where both eyes of a subject are enrolled. In the eCRF these visits will be noted with wording of "2nd Eye" instead of A. For example: Visit 1A will be shown as Visit 1-2nd Eye.

 Required at certain visits for cases of exacerbated post-surgical intraocular inflammation. See Manual of Procedures for details on requirements for which visit(s) testing is required.

 Concomitant medications and medical history must be fully documented in the subject source documents. CRF data will be Targeted:

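### Does censoring rule 2 clash with the visit schedule, or leave open whose second surgery triggers it, in a way that matters?

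*SAP*

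**What the plan says.** Section 5.3.1 plans Kaplan-Meier estimates at 180 days as sensitivity analyses under two censoring rules. Rule 1 keeps the full follow-up of both eyes. Rule 2 begins "If a subject has a second cataract surgery within 180 days of the occurrence of the first cataract surgery" and then says that "the follow-up for the first eye will be censored at the time of second surgery", provided no inflammation came first. It applies to first-eye rates only. The same section carries the approach over to the secondary endpoints: "Cumulative event rates at 180 days will be provided using Kaplan-Meier estimator as described above for first eyes, second eyes, and overall eyes".

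Three other places bear on this:

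- **Section 12, Table 12-1.** The screening column reads "Visit 0 (≤ 40 days pre-surgery 1st eye, ≤ 60 days pre-surgery 2nd eye", and there is no matching visit for the second eye. The visits marked A are "for cases where both eyes of a subject are enrolled". Section 1.2 says subjects "attend a total of up to 11 scheduled visits".
- **Section 2.2.** The safety set holds every eye with an attempted study-lens implantation. Second surgeries within 6 months count, and "Second eye surgeries after 6 months of the first surgery are also included".
- **Section 5.3.2.** A listing is planned for "Ocular Adverse Events from Non-Study Eyes", so the SAP expects some fellow eyes to be outside the study.

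**The concern.** Two things look wrong at first.

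1. **Timing.** If one Visit 0 serves both eyes and must fall within 60 days of the second surgery, two study-eye surgeries cannot be 180 days or 6 months apart. Rule 2 and Section 2.2 then seem to be written for a schedule that the study does not have.
2. **Trigger.** Rule 2 speaks of a subject's second cataract surgery without restricting it to an enrolled eye. A subject with one study eye may later have the other eye operated on outside the study. On a literal reading that surgery censors the study eye; on a study-eye reading it does not. Two programmers could get different first-eye estimates from the same data.

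There is also a question of support. If only study eyes count, every event-free first eye of a bilateral subject is censored by Day 60. The rest of the 180-day curve then rests on one-eye subjects, whose number the SAP does not give.

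**Working it through.** **Visit count.** One Visit 0 plus, for each eye, one surgery and four follow-up visits: 1 + 2 × (1 + 4) = 11. This matches Section 1.2. A separate Visit 0 for the second eye would give 12, so Visit 0 is single.

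**Longest on-schedule gap.** Put Visit 0 on day 0. The first surgery falls on days 0 to 40 and the second by day 60. The longest gap is 60 − 0 = 60 days; it is 60 − 40 = 20 days if the first surgery is on day 40.

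**Against rule 2.** Every gap of 0 to 60 days is within 180 days, so the rule applies as written. A second surgery after Day 180 could not shorten follow-up that is read at Day 180, so the limit is the analysis horizon.

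**Against Section 2.2.** No on-schedule pair is more than 6 months apart, so that sentence has no on-schedule case. But it sets inclusion, not timing. Together with the sentence before it, it takes in second eyes whatever the gap and leaves none unassigned.

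**Support under rule 2.** Inputs: 3,300 eyes (Section 1.2) and a bilateral share b, which is assumed. First eyes = 3,300/(1 + b). If only study eyes trigger the rule, first eyes × (1 − b) remain after Day 60. For Day 150, assume that exits at Visit 4 are uniform over Days 90 to 180 and that nobody drops out earlier; multiply by (180 − 150)/90 = 1/3. Events are ignored in these counts.

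| b | First eyes | After Day 60, rule 2 | Day 150, rule 1 | Day 150, rule 2 |
|---|---|---|---|---|
| 20% | 2,750 | 2,200 | 917 | 733 |
| 50% | 2,200 | 1,100 | 733 | 367 |
| 80% | 1,833 | 367 | 611 | 122 |
| 90% | 1,737 | 174 | 579 | 58 |

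Late support falls under both rules. Whether it is thin under rule 2 depends on b.

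**Effect of the trigger.** Constructed case: four first-eye events before any second surgery, and one between Days 60 and 90 in a one-eye subject whose non-study eye has already had surgery. Let n1 be the number of first eyes and n2 the number left after Day 60.

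- Study eyes only: 1 − (1 − 4/n1)(1 − 1/n2)
- Any second surgery: 4/n1, since the late event is censored
- Rule 1: 1 − (1 − 4/n1)(1 − 1/(n1 − 4)) = 5/n1

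For b = 50%: 1 − (1 − 4/2,200)(1 − 1/1,100) = 2.73 per 1,000, against 4/2,200 = 1.82; rule 1 gives 5/2,200 = 2.27.

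| b | Rule 2, study eyes only | Rule 2, any surgery | Difference | Rule 1 |
|---|---|---|---|---|
| 20% | 1.91 | 1.45 | 0.46 | 1.82 |
| 50% | 2.73 | 1.82 | 0.91 | 2.27 |
| 80% | 4.90 | 2.18 | 2.72 | 2.73 |
| 90% | 8.04 | 2.30 | 5.74 | 2.88 |

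**For scale.** Section 9 gives a 95% interval width of 3.6 per 1,000 at an observed rate of 2 with 3,000 eyes. The exact interval for 6/3,000 is 0.73 to 4.35, a width of 3.61, so that figure reproduces. The differences in the table stay below this width up to b = 80% and exceed it at 90%.

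**The case for a change.** The best argument for a change is about the trigger. A censoring rule belongs in the SAP and cannot be left to the protocol. Sections 2.2 and 5.3.1 spell out the condition that both eyes are enrolled when they mean it, and rule 2 does not. The literal wording covers any eye, non-study eyes are expected, and a short clause would settle it. With many bilateral subjects, one late event could shift the estimate visibly.

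The observation about the wording stands; the need for a change does not. Rule 2 sits beside rule 1, which concerns both eyes, in a section that reports first, second and overall eyes from a set holding only eyes with an attempted study-lens implantation. Table 12-1 schedules a second-eye surgery visit only where both eyes are enrolled. An analyst would take the second surgery to be that visit. The large contrast needs a 90% bilateral share and one event in a particular window, in a particular kind of subject; nothing in the SAP suggests that such an event is likely.

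The lack of an on-schedule case for the 6-month sentence also stands. But Section 2.2 applies to both cohorts, and Cohort 1 was implanted before Amendment 7, perhaps under other visit windows; the protocol is not at hand to settle this. Section 2 also refers to a deviation and evaluability plan, so out-of-window surgeries are foreseeable. A catch-all that is seldom or never used changes no result.

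First-eye numbers at risk would help a reader of the curves, but that is a reporting preference.

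**Conclusion.** No change follows. The 180-day limit in rule 2 does not conflict with Table 12-1. The 6-month sentence in Section 2.2 is redundant on the current schedule but misassigns no eye; this review takes no position on which interval between surgeries is right. The unstated trigger is a gap in wording that the surrounding definitions fill, with study eyes as the natural reading.

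The possible effect is confined to the rule 2 first-eye estimates for the primary and secondary endpoints. In the constructed case the two readings differ by 0.46 to 5.74 per 1,000 for assumed bilateral shares of 20% to 90%, with 3,300 eyes and no dropout before Day 90. Without an event that the two readings treat differently, they differ only through the numbers at risk. The study has no formal hypotheses (Section 5.2), and the primary rate uses full follow-up of both eyes, so the primary result and the conclusion are the same on either reading.

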# 1.5 Interim Analysis

Interim reports pertaining to the progress of the post-approval study will be submitted to the FDA for review every six months up to the first two years, or as requested, starting from the date of FDA approval of the ReSTOR +3.0 D Toric intraocular lens, and will continue to be submitted annually thereafter until study completion.

For each interim report, the number of eyes enrolled, the number of eyes with an attempted implantation and the number of eyes with successful implantation of the ACRYSOF IQ RESTOR study IOLs will be reported. In addition, the rates for post-surgical intraocular inflammation, Toxic Anterior Segment Syndrome (TASS), acute postoperative endophthalmitis, chronic postoperative endophthalmitis, and uncategorized cases of post-surgical intraocular inflammation (based upon the specified case definition) will be reported, and a listing of all such events will be provided. A listing of all ocular serious adverse events will also be provided.

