#### 5 SAFETY ANALYSIS STRATEGY

# 5.1 Safety Endpoints

The primary safety endpoint is the rate (per 1,000 IOL implants) of post-surgical intraocular inflammation (based upon the specified case definition) reported within a 180-day post-surgical period following attempted implantation of study IOLs for Cohort 2.

The secondary safety endpoints are the rates (per 1,000 IOL implants) of Toxic Anterior Segment Syndrome (TASS), acute postoperative endophthalmitis, chronic postoperative endophthalmitis, and uncategorized cases of post-surgical intraocular inflammation (based

upon the specified case definition), respectively, reported within a 180-day post-surgical period following attempted implantation of study IOLs for Cohort 2.

Other safety endpoints for Cohort 2 are:

- Adverse events
- Device deficiencies
- Problems during surgery
- Other surgical procedures during surgery
- Best Corrected Distance Visual Acuity (BCDVA)
- Intraocular Pressure (IOP)
- Slit lamp observations that include, but not limited to:
  - o Hypopyon
  - Corneal precipitates granulomatous
  - o Corneal precipitates non-granulomatous
  - o Fibrin in the anterior chamber, on the surface of the iris or on the IOL
- Fundus observations
- Slit lamp examinations
  - o Aqueous cell
  - Aqueous flare
  - Eyelid edema
  - Conjunctival hyperemia
  - Ciliary flush
- Corneal Assessment
  - Corneal edema

- Corneal haze
- Evaluation of vitreous cells
- Evaluation of vitreous haze
- Culture of ocular media
- Subject Reported Symptoms

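### Type-specific inflammation rates count a multi-type eye under one type only, so each secondary rate can understate how many eyes had that type

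*SAP*

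**What the plan says.** Section 5.1 of the SAP defines the secondary endpoints type by type: "The secondary safety endpoints are the rates (per 1,000 IOL implants) of Toxic Anterior Segment Syndrome (TASS), acute postoperative endophthalmitis, chronic postoperative endophthalmitis". A fourth rate covers inflammation that fits none of these. Nothing there ranks the types or makes a rate depend on device attribution.

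Section 5.3.1 gives the counting rule for an eye with more than one type: "An eye with multiple different types of inflammation is only counted once; the inflammation related to device will take precedence". Where device attribution does not settle the matter, a fixed ranking applies, with TASS first, then acute, then chronic endophthalmitis, and the residual group last. The resulting rates "will be estimated for first eyes, second eyes, and overall eyes along with the exact two-sided 95% confidence intervals". The rate formula, written out for the primary endpoint, is "Total # of reported events/Total # of attempted implants x 1,000"; the secondary rates are on the same per-1,000-implants scale.

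Two other outputs in the same section bear on this. One concerns causality: "Inflammations related to the device will also be reported". The other is a listing of affected eyes, "where all multiple inflammations that occurred in one eye will be listed". Section 1.5 promises the same kind of output for interim reports: "a listing of all such events will be provided".

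**The concern.** The endpoint as named is the rate of eyes with a given type. The quantity computed is the rate of eyes assigned to that type after a ranking. The two differ as soon as one eye has two types, a case the SAP foresees because it writes a rule for it.

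The difference has one direction. A displaced eye remains among the attempted implants but leaves the numerator of the displaced type. In a surveillance study, too low is the unfavourable direction.

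The device-first rule adds a second problem. If the lower-ranked type is judged device-related and the higher-ranked one is not, the higher-ranked diagnosis drops out of its own rate. TASS judged unrelated to the device, in an eye that also has a device-related type, is not counted as TASS. A causality judgement then alters a diagnosis rate, although device-related inflammation is already reported separately.

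**Working it through.** **Inputs.** Section 9 uses N = 3,000 eyes and an example rate of 2 per 1,000. Section 1.2 gives about 3,300 eyes. The counting rule and rate formula are in Section 5.3.1. The SAP gives no frequency of multi-type eyes and no split between first and second eyes, so those are varied or assumed below.

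**1. Reproduce the SAP's own figure.** The exact (Clopper-Pearson) limits for x events in n eyes are the 2.5% quantile of Beta(x, n − x + 1) and the 97.5% quantile of Beta(x + 1, n − x). For x = 6, n = 3,000 (2 per 1,000) they are 0.73 to 4.35 per 1,000, width 3.61. This agrees with the 3.6 in Section 9. That example amounts to only 6 inflamed eyes across all four types.

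**2. Shift per displaced eye.** Shortfall = m × 1,000 / n, where m is the number of eyes displaced from one type (assumed).

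| m | n = 3,000 | n = 3,300 |
|---|---|---|
| 0 | 0 | 0 |
| 1 | 0.33 | 0.30 |
| 2 | 0.67 | 0.61 |
| 3 | 1.00 | 0.91 |

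**3. First and second eyes.** Assume each subject's first enrolled eye is a first eye. With 3,000 eyes, the first-eye denominator lies between 1,500 (all subjects bilateral) and 3,000 (none bilateral), and the second-eye denominator is at most 1,500. One displaced eye then moves the first-eye rate by 0.33 to 0.67 per 1,000, and the second-eye rate by at least 1,000/1,500 = 0.67.

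**4. Effect on a reported rate and interval** (one displaced eye, assumed counts, n = 3,000, per 1,000):

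| Eyes that had the type | Rate counting every such eye | Rate under the SAP rule |
|---|---|---|
| 2 | 0.67 (0.08 to 2.41) | 0.33 (0.01 to 1.86) |
| 1 | 0.33 (0.01 to 1.86) | 0.00 (0.00 to 1.23) |

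**5. Which types can lose an eye.** Four types give 6 pairs. Each pair has 4 attribution patterns: neither type device-related, both, only the higher-ranked, only the lower-ranked. That makes 24 cases. The SAP does not say what happens when both types are device-related; I assume the fixed order then applies.

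- The lower-ranked type is displaced in 3 of 4 patterns: 6 × 3 = 18 cases.
- The higher-ranked type is displaced only when the lower-ranked type alone is device-related: 6 × 1 = 6 cases.
- Each type appears in 12 cases. TASS is displaced in 3 × 1 = 3; acute in 3 + 2 × 1 = 5; chronic in 2 × 3 + 1 = 7; uncategorized in 3 × 3 = 9.

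These are counts of cases, not probabilities. They show that every type, including TASS, can be understated, and that the lower ranks are exposed more often.

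**6. Six-eye illustration** (assumed). Take 6 inflamed eyes of 3,000, none device-related: one TASS only, one acute only, one uncategorized only, one TASS with acute, one acute with chronic, one chronic with uncategorized. The SAP rule gives counts of 2, 2, 1, 1 (sum 6, the primary count). Counting each type an eye had gives 2, 3, 2, 2 (sum 9). Acute goes from 0.67 to 1.00 per 1,000; chronic and uncategorized each go from 0.33 to 0.67.

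**The case against.** The strongest reply is that Sections 5.1 and 5.3.1 do not contradict each other. Section 5.1 is silent on multi-type eyes, and a methods section may fill that silence. A residual class called uncategorized suits a mutually exclusive split that adds up to the primary count. The rule is pre-specified, the study tests no hypothesis (Section 5.2), and the listing lets a reader recount. Whether one eye can meet two definitions within 180 days depends on a case definition not set out in the SAP. Finally, Section 5.3.2 tabulates ocular adverse events by preferred term, once per eye per term, with exact intervals and no hierarchy.

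Much of this stands as a limit on importance. The exclusive split is a legitimate display, the effect is zero if no eye has two types, and hand recounting is feasible with few cases.

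It does not remove the point. Pre-specifying the rule does not turn an assigned-type rate into the rate named in Section 5.1. The listings carry no rate or interval. The adverse event table is organised by preferred term, and the SAP nowhere maps those terms to the four case-definition types, so it gives partial cover at best. It also shows that the SAP already counts without a hierarchy elsewhere.

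**Conclusion.** The concern holds. Whenever an eye has two types, the rate and exact interval for the displaced type do not describe the secondary endpoint as Section 5.1 words it, and the error can only be downward. The size is 0.33 per 1,000 per displaced eye at 3,000 eyes (0.30 at 3,300), and at least 0.67 for second eyes at 3,000 under the split assumption above. With so few expected events, one eye can halve a type's rate or take it to zero.

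This assumes that the attempted-implant denominator applies to the secondary rates and that at least one multi-type eye occurs; the SAP does not allow the likelihood of that to be estimated. The primary rate is unaffected and no test depends on these rates. The change is worth making because it is cheap and concerns named secondary endpoints.

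**What to change.** In Section 5.3.1, for each secondary rate and its exact interval (overall, first eyes, second eyes), count an eye once if it had at least one event of that type within 180 days, whatever other types it had and whatever the device attribution. Leave the separate device-related reporting as planned.

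Keep the ranked, mutually exclusive breakdown as a supplementary table, labelled as such and adding up to the primary count. State there how an eye with two device-related types is placed. Say also which counting rule the type-specific Kaplan-Meier estimates follow, since the SAP does not.

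The cost is a change of wording, one table and a footnote; no new data are needed. The one drawback is that the four rates may sum to more than the primary rate, by 0.33 per 1,000 for each extra type in an eye at 3,000 eyes (0.30 at 3,300). The footnote should say so.
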